#### **Reasons for SVR12 Non-response**

Subjects who do not achieve SVR (SVR12 non-responders) will be categorized as having:

1. On-treatment virologic failure (see **On-treatment virologic failure** definition);
2. Relapse (defined according to the **Relapse12** definition for subjects who complete treatment);
3. Prematurely discontinued study drug with no on-treatment virologic failure (defined as any SVR12 non-responder who prematurely discontinued study drug and did not meet the **On-treatment virologic failure** definition);
4. Missing follow-up data in the SVR12 window defined as any subject who completed study drug without data in the SVR12 window after applying the imputation rules and not meeting the definitions of (1), (2), or (3)];
5. Other (defined as any SVR12 non-responder not meeting the definitions of (1) – (4), such as a subject with a single quantifiable value within the SVR12 window followed by an undetectable value beyond the SVR12 window).

## Reasons for SVR24 Non-response

Subjects who do not achieve SVR (SVR24non-responders) will be categorized as having:

1. On-treatment virologic failure (see **On-treatment virologic failure** definition);
2. Relapse12;
3. Relapse24;
4. Prematurely discontinued study drug with no on-treatment virologic failure (defined as any SVR24 non-responder who prematurely discontinued study drug and did not meet the On-treatment virologic failure definition);
5. Missing follow-up data in the SVR24 window defined as any subject who completed study drug without data in the SVR24 window after applying the imputation rules and not meeting the definitions of (1), (2), (3) or (4)];
6. Other (defined as any SVR24 non-responder not meeting the definitions of (1) – (5), such as a subject with a single quantifiable value within the SVR24 window followed by an undetectable value beyond the SVR24 window).

## 10.2 Primary Efficacy Analysis

The primary efficacy endpoint is the percentage of subjects with sustained virologic response 12 weeks after the last actual dose of study drug (including DAA, pegIFN, and RBV) (SVR12; HCV RNA < LLOQ 12 weeks after the last actual dose of study drug). The percentage of subjects with SVR12 and the corresponding 95% Wilson score confidence interval will be calculated.

## 10.3 Secondary Efficacy Analyses

The secondary efficacy endpoints are the percentage of subjects with sustained virologic response 24 weeks after the last actual dose of study drug (including DAA, pegIFN, and RBV) (SVR24; HCV RNA < LLOQ 24 weeks after the last actual dose of study drug) and the percentage of subjects with eRVR (HCV RNA < LLOQ at TI Weeks 4 through 12).

The percentage of subjects with SVR24 and eRVR and the corresponding 95% Wilson score confidence intervals will be calculated.

A subject will be considered to have e RVR if after all missing data are imputed according to rules specified in Section 6.0, he/she has HCV RNA levels below LLOQ at TI Week 4 and TI Week 12 with no confirmed HCV RNA  $\geq$  LLOQ in between. If a subject is missing HCV RNA data at either TI Week 4 or 12 then the subject will be considered an eRVR failure.

#### **10.4 Sensitivity Analyses for SVR**

A sensitivity analysis of SVR12 will be conducted using a Modified Intent-to-Treat Genotype and Virologic Failure (mITT-GT -VF) population. The number and percentage of subjects in the mITT-GT-VF population achieving SVR12 and the corresponding 95% Wilson score confidence interval will be calculated.

#### **10.5 Additional Efficacy Analyses**

The following additional efficacy endpoints will be summarized for the overall treatment group as specified:

- the percentage of subjects with unquantifiable HCV RNA at each post-baseline visit throughout the Substudy 1 using data from the central laboratory as observed (i.e., no imputation for missing data);
- the percentage of subjects with RVR (per RVR definition);
- the percentage of subjects with Final Treatment Visit response (per Final Treatment Visit response definition);
- the percentage of subjects achieving SVR4;
- the percentage of subjects with on-treatment virologic failure (per on-treatment virologic failure definition);
- the percentage of subjects who experienced Relapse12 (per Relapse12 definition);

- the percentage of subjects who experienced Relapse24 (per Relapse24 definition);
- the percentage of subjects who achieved SVR24 who subsequently relapsed (Relapselate);
- the percentage of subjects who experienced Relapseoverall (per Relapseoverall definition).

The percentage of subjects with RVR, Final Treatment Visit Response, SVR, on-treatment virologic failure and post-treatment relapse will be calculated with two-sided 95% confidence intervals using the Wilson score method. Imputation methods, as described in Section 6.0, will be used when summarizing each of these endpoints.

The number and percent of subjects who achieve SVR12 will be presented along with the number of subjects who do not achieve SVR12 by reason for non-response (defined in Section 10.1). The non-responders will be presented in a listing. Similarly, the number and percent of subjects who achieve SVR24 will be presented along with the number of subjects who do not achieve SVR24 by reason for non-response (defined in Section 10.1). The non-responders will be presented in a listing.

The concordance between SVR12 and SVR24 will be assessed by the agreement between SVR12 and SVR24 and by the positive predictive value (PPV) and negative predictive value (NPV) of SVR12 on SVR24. The agreement between SVR12 and SVR24 is a percentage defined as the number of subjects achieving both SVR12 and SVR24 and the number of subjects not achieving both SVR12 and SVR24 out of all subjects in the ITT population. The PPV of SVR12 on SVR24 is the proportion of subjects who achieve SVR12 and SVR24 out of all subjects who achieved SVR12. The NPV of SVR12 on SVR24 is the proportion of subjects who do not achieve SVR12 and SVR24 out of all subjects who did not achieve SVR12.

The number and percentage of subjects who fail to suppress HCV RNA and received at least 6 weeks of treatment (study drug duration  $\geq$  36 days) will be tabulated per treatment arm along with the subject numbers corresponding to the subjects who failed to suppress.

The number of subjects who breakthrough at any time during treatment and within each protocol-specified visit (defined in Table 1 and Table 2) will be summarized along with a corresponding listing displaying the subject numbers at the first occurrence of breakthrough.

The number of completers (defined as DAA duration  $\geq$  161 days and pegIFN/RBV duration  $\geq$  252 days) who relapse within the SVR4 window, within the SVR12 window, within the SVR24 window (defined in Table 3), outside of the SVR24 window (PR end day > 210), and anytime post-treatment, Relapseoverall, (study drug end day  $\geq$  2) will be summarized along with a corresponding listing displaying the first occurrence of relapse. A similar table and listing will be provided of Preterm Relapses for subjects who prematurely discontinued study drug (defined as DAA duration < 161 days and/or pegIFN/RBV duration < 252 days).

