## **5.0 Analysis Populations**

### **5.1 Definition for Analysis Populations**

#### **Intent-to-Treat (ITT) Population**

The intent-to-treat (ITT) population will consist of all enrolled subjects who receive at least one dose of study drug. Efficacy analyses will be performed on the ITT population.

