### 6.3 Definition of Missing Data Imputation

Imputations for missing data will be performed when analyzing RVR, Final Treatment Visit Response, eRVR, and all SVR endpoints.

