#### HCV RNA

HCV RNA values will be selected for analysis based on the analysis windows defined in Section 6.2. When there is no HCV RNA value in a defined visit window, the closest values before and after the window will be used for flanking imputation, regardless of the value chosen for the subsequent and preceding window.

For flanking imputation, if a subject has a missing HCV RNA value at a post-baseline visit but with undetectable or unquantifiable HCV RNA levels at both the preceding value and the succeeding value, then the HCV RNA level will be imputed as undetectable or

unquantifiable, respectively, at this visit for this subject. In addition, if a subject has an unquantifiable HCV RNA level at the preceding value and an undetectable HCV RNA level at the succeeding value, or vice versa, the HCV RNA level will be imputed as unquantifiable at this visit for this subject.

For analyses of SVR, subjects still missing visit values after flanking imputation will have backward imputation applied. For backward imputation, if the nearest HCV RNA value after the SVR window is unquantifiable or undetectable, then it will be used to impute the HCV RNA value in the SVR window.

For analyses of RVR, Final Treatment Visit Response, eRVR, and SVR, subjects still missing a value for the visit window associated with the analysis after performing the imputations described above will be imputed as a failure.

If a subject starts another treatment for HCV, then all HCV RNA values for this subject measured on or after the start date of the new HCV treatment will be excluded from analyses. The subject will be considered a failure for summaries of viral response at all time points after the start of the new HCV treatment.

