**Relapse12** = confirmed HCV RNA  $\geq$  LLOQ between Final Treatment Visit and 12 weeks after last actual dose of study drug (up to and including SVR12 assessment time point) for a subject with HCV RNA  $<$  LLOQ at the Final Treatment Visit who completes treatment. Completion of treatment is defined as DAA duration  $\geq 161$  days and pegIFN/RBV duration  $\geq 252$  days.

**Relapse24** = confirmed HCV RNA  $\geq$  LLOQ within the SVR24 window for a subject who achieved SVR12 and has HCV RNA data available in the SVR24 window.

**Relapseoverall** = confirmed HCV RNA  $\geq$  LLOQ between Final Treatment Visit and up to and including the last HCV RNA measurement collected in the PT Period for a subject with HCV RNA  $<$  LLOQ at Final Treatment Visit who completes treatment. Completion of treatment is defined as DAA duration  $\geq$  161 days and pegIFN/RBV duration  $\geq$  252 days.

**Relapselate** = confirmed HCV RNA  $\geq$  LLOQ at any time after the SVR24 assessment time point for a subject who achieved SVR24 and has post-SVR24 HCV RNA data available.

If the last available post-treatment value is  $\geq$  LLOQ, then the subject will be considered a relapse (i.e., will not require confirmation). Relapse analyses will exclude subjects who do not have any post-treatment HCV RNA values.

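### SVR12/SVR24 concordance is computed on imputed statuses in all ITT subjects, so imputation and loss to follow-up can create agreement or discordance that says nothing about relapse

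*SAP*

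**What the plan says.** SAP 10.5 defines three concordance measures. Agreement is the share of subjects with the same result on both endpoints, "out of all subjects in the ITT population". PPV is the share who also achieve SVR24 "out of all subjects who achieved SVR" at 12 weeks, and NPV is the matching share among SVR12 non-achievers. SAP 5.1 defines the ITT population as "all enrolled subjects who receive at least one dose of study drug".

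The statuses entering these measures are imputed. SAP 6.3 states: "Imputations for missing data will be performed when analyzing RVR, Final Treatment Visit Response, eRVR, and all SVR endpoints". For an empty window the order is:

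1. Flanking: "the closest values before and after the window will be used for flanking imputation". If both are below LLOQ, the window is imputed below LLOQ.
2. Backward, for SVR only: if the nearest value after the window is unquantifiable or undetectable, "then it will be used to impute the HCV RNA value in the SVR window".
3. Failure: a subject still missing "after performing the imputations described above will be imputed as a failure".

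SAP 10.5 neither restricts the concordance measures to observed data nor asks for a count of imputed statuses. By contrast, the Relapse24 definition in SAP 10.1 covers a subject who achieved SVR12 "and has HCV RNA data available in the" SVR24 window.

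**The concern.** A concordance analysis asks whether the 12-week result foretells the 24-week result. It can answer only where both results were measured, or where earlier data already settle them. When one sample supplies both statuses, the pair carries no information on prediction. When a status is set to failure because no sample exists, the pair records attendance, not virology.

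The distortions run in different directions. Loss after week 12 lowers PPV and agreement. Loss before week 12 and shared imputation push agreement up. The net effect on agreement therefore cannot be signed in advance. With enrollment of up to 35 (Protocol 1.2), one or two subjects move the percentages visibly. PPV can also sit beside a Relapse24 rate that appears to contradict it.

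**Working it through.** The documents give no expected agreement, PPV or NPV, so there is no planned figure to reproduce. The check applies the SAP rules to possible visit patterns and then sizes the effect.

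**Inputs**
- SVR12 window: Study Drug End Days 57 to 126. SVR24 window: days 127 to 210, directly following. The last value in a window is used (SAP 6.2, Table 3).
- HCV RNA is scheduled at PT Weeks 2, 4, 8, 12, 24, 36 and 48 (Protocol Table 7).
- SVR also requires no confirmed quantifiable post-treatment value before or during the window (SAP 10.1).
- Imputation order: flanking, backward, failure (SAP 6.3).

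**Step 1: all patterns.** Each of the seven visits is below LLOQ, at or above LLOQ, or missing, giving 3^7 = 2,187 patterns. The Final Treatment Visit is taken as below LLOQ. Counts show how the rules behave; they are not probabilities.

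*PT Week 12 missing (3^6 = 729 patterns).* SVR12 is filled by flanking or backward imputation in 351, and the two endpoints agree in all 351 (273 both achieved, 78 both failed because of an earlier confirmed value). In the other 378, SVR12 is set to failure because the next value is quantifiable or absent. SVR24 then fails for the same reason, so these agree too. The only break found needs a second, unscheduled sample in days 127 to 210, for example below LLOQ at day 150 and quantifiable at day 190.

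*PT Week 24 missing (729 patterns).*

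| SVR12 | SVR24 after the rules | Patterns | Scored as |
|---|---|---|---|
| Achieved | Achieved (136 flanking + 32 backward) | 168 | Agreement |
| Achieved | Failed: no later value, or next value quantifiable | 105 | Discordance |
| Not achieved | Failed, imputed as failure | 300 | Agreement |
| Not achieved | Failed despite a filled window (76 + 28) | 104 | Agreement |
| Not achieved | Achieved by backward imputation | 52 | Discordance, other direction |

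The total is 168 + 105 + 300 + 104 + 52 = 729. Of the 105 discordant patterns, 21 have no later value and so no evidence of relapse. The other 84 have a quantifiable next value after day 210.

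**Step 2: PPV.** Let r be SVR12 achievers and m those with no HCV RNA value from day 127 onward, with no relapse. PPV as written = (r − m)/r. On observed data, PPV = (r − m)/(r − m) = 100%.

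Take r = 28 as an assumption:
- m = 1: 27/28 = 96.4%
- m = 2: 26/28 = 92.9% (Wilson 77.4 to 98.0), against 26/26 = 100% (87.1 to 100)
- m = 4: 24/28 = 85.7%

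For m = 2, Relapse24 in the same report is 0/26, because the two lost subjects have no data in the SVR24 window.

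**Step 3: agreement.** With N = 35 and no other discordance, agreement = (35 − m)/35: 97.1%, 94.3% and 91.4% for m = 1, 2 and 3. Each such subject costs 1/35 = 2.9 points.

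**Step 4: loss before week 12.** Let b be non-achievers whose two statuses are observed, a of them also SVR24 failures, and k further subjects lost before week 12 with no later value. NPV as written = (a + k)/(b + k), which exceeds a/b whenever a < b. The k subjects enter agreement as concordant pairs in the same way.

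**The case against.** The strongest reply is that the imputation rules are less crude than they look. A reader might infer that any missed week 24 visit counts as discordance. The documents do not support that. Failure is the last step, after flanking and backward imputation; PT Weeks 36 and 48 are scheduled; and Protocol 5.1.4 asks subjects leaving Substudy 3 early to return for a discontinuation visit. An SVR12 achiever who misses week 24 and is below LLOQ at the next value is an SVR24 success and concordant. The 26/28 example therefore holds only for subjects with no usable value from day 127 onward, and the documents give no rate for that.

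A reader might also infer that PPV must conflict with Relapse24, or that the fix would make them match. Neither follows. They can differ, but they can do so with complete data: Relapse24 generally needs confirmation, while SVR24 can fail on a single quantifiable last value in its window.

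Third, SAP 10.5 already tabulates and lists SVR24 non-responders by reason, with missing follow-up as its own category. This helps only in part. That category is limited to subjects who completed study drug, so missing data in early discontinuers fall under premature discontinuation. The listings also cover non-responders only, so successes reached by imputation are not shown.

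Finally, requiring an observed value in both windows would drop known failures, such as a confirmed early relapse followed by retreatment, after which HCV RNA is excluded. That stands, and the fix is worded to keep them.

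**Conclusion.** The point holds as a limited defect in a descriptive additional analysis. On scheduled visits, an SVR12 status imputed from the next later value agrees with SVR24 by construction. An SVR12 achiever with an empty SVR24 window and no later value below LLOQ is scored as discordant. Where there is no later value at all, PPV falls without evidence of relapse. A subject lost before week 12 with no later value is a concordant negative, which raises agreement and NPV unless they are already 100%.

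Under the stated assumptions (28 achievers, 1 to 4 with no value from day 127 onward, no relapse), PPV runs from 96.4% down to 85.7% where observed data would give 100%. The true size depends on follow-up losses that the documents do not give. The SVR12 and SVR24 rates, including the primary result, do not change.

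**What to change.** In SAP 10.5, compute agreement, PPV and NPV in subjects whose SVR12 and SVR24 statuses are both determined by observed HCV RNA. That means a value in the window, or an earlier confirmed post-treatment value at or above LLOQ that already establishes failure. Apply no flanking, backward or missing-as-failure imputation to these measures. Report the number of subjects excluded and the number of SVR12 and SVR24 statuses that were imputed.

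The all-ITT version may stay alongside, labelled as based on imputed statuses, and ITT imputation stays for the SVR rates themselves.

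The cost is one sentence and no new data. The downside is a slightly smaller denominator. Subjects with no post-treatment HCV RNA, including any with on-treatment virologic failure, would be among those excluded, which is why the count should be shown.

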## 10.6 Resistance Analyses

The genes of interest for population sequencing in this study are those encoding full length NS3/4A and NS5A, while for clonal sequencing they are those encoding NS3 amino acids 1 to 181 and NS5A amino acids 1 to 215. For each DAA target, signature amino acid positions are 1) for paritaprevir: 36, 43, 55, 56, 80, 155, 156, and 168 in NS3 for genotype 1a; 55, 56, 155, 156, and 168 in NS3 for genotype 1b; and 2) for ombitasvir: 24, 28, 29, 30, 31, 32, 58, 62, 92, and 93 in NS5A for genotype 1a; 24, 28, 29, 30, 31, 32, 58, 62, 92, and 93 in NS5A for genotype 1b. The prototypic reference sequences used for analysis will be H77 for genotype 1a or Con1 for genotype 1b. Only samples with an HCV RNA level of  $\geq$  1000 IU/mL will undergo sequence analysis in order to allow accurate assessment of products of amplification. Therefore, if the HCV RNA level at the time of virologic failure is < 1000 IU/mL, the sample closest in time after the failure with an HCV RNA level  $\geq$  1000 IU/mL will be used. Clonal sequencing of a given target will be performed only if no variants are detected at signature amino acid positions by population sequencing in that sample. In addition, clonal sequencing may be performed if there is a complex mixture of amino acids at one or more signature position that cannot be resolved by population sequencing.

Included time points for analyses on samples from subjects who experience virologic failure (as defined in Section 5.4.1.1) are (1) time of virologic failure or sample closest in time after failure with an HCV RNA level of  $\geq 1000$  IU/mL, (2) 24 weeks post-DAA treatment, provided that variants at signature amino acid positions were detected by either population or clonal sequencing at the time of failure, and (3) 48 weeks post-DAA treatment, provided that variants at signature amino acid positions were detected by either population or clonal sequencing at post-DAA treatment Week 24.

The following definitions will be used in the resistance analyses:

- Baseline variant: a variant (by population sequencing) in a baseline sample determined by comparison of the amino acid sequence of the baseline sample to the appropriate prototypic reference amino acid sequence for a given DAA target (NS3 or NS5A).
- Post-baseline variant by population sequencing: an amino acid variant in a post-baseline time point sample that was not detected at baseline and is detectable by population sequencing.
- Post-baseline variant by clonal sequencing: a variant relative to prototypic reference sequence at a signature amino acid position by clonal sequencing in at least 2 clones from that sample (among the subset of subjects for whom clonal sequencing is performed).
- Emerged variant by population sequencing: a post-baseline variant that is observed in 2 or more subjects of the same HCV subtype by population sequencing.
- Linked variant by population sequencing: 2 or more signature or emerged amino acid variants identified within a target by population sequencing, where at least one of the variants is at a signature position, and no mixture of amino acids is detected at either position.

For those subjects whose baseline sample has an HCV RNA level  $\geq 1000$  IU/mL, a listing by subject of all baseline variants relative to prototypic reference sequence at signature amino acid positions will be provided for each DAA target (NS3 and NS5A).

The following analyses will be performed on the samples from subjects who experienced virologic failure and have post-baseline resistance data available.

The HCV amino acid sequence as determined by population sequencing will be compared with the baseline and appropriate prototypic reference amino acid sequences. Listings by subject of all post-baseline variants detected by population sequencing relative to the baseline amino acid sequences will be provided for each DAA target (NS3 and NS5A). In addition, listings by subject of variants detected by population sequencing at signature amino acid positions relative to baseline and the appropriate prototypic reference amino acid sequences will be provided.

For the subset of samples for which clonal sequencing is performed, the amino acid variants determined by clonal sequencing will be summarized by counting the number of clones whose amino acid sequence does not match that of the prototypic reference sequence by subject at each time point and amino acid position, out of the total number of clones analyzed. Listings by subject of post-baseline variants at signature positions detected by clonal sequencing will be provided for each DAA target.

Linkage between emerged or signature variants by population sequencing will also be evaluated. A listing by subject and time point of the linked variants by population sequencing for each target will be provided.

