5.3.3.3 Resistance Variables

The following resistance analyses will be performed for subjects who do not achieve SVR: the variants at each amino acid position identified by population and/or clonal nucleotide sequencing (1) at baseline will be compared to the appropriate prototypic reference sequence, and (2) at available post-baseline time points will be compared to baseline and the appropriate prototypic reference sequences.

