5.4.1.1 Virologic Failure Criteria

During the Treatment Period and Follow-up Period of the study, the virologic data will be reviewed by the investigator to evaluate if subjects have met virologic failure criteria.

The following criteria will be considered evidence of virologic failure:

- Failure to achieve HCV RNA level $< 1,000$ IU/mL at TI Week 4. Subject will stop all DAAs and continue pegIFN and RBV at the investigator's discretion.
- Failure to achieve at least a $2 \log_{10}$ IU/mL HCV RNA reduction from baseline at TI Week 12. Subject will stop all study drugs.
- HCV RNA ≥ 25 IU/mL at TI Week 24. Subject will stop all study drugs.
- Confirmed HCV RNA increase of $> 1 \log_{10}$ from nadir (defined as 2 consecutive HCV RNA measurements $> 1 \log_{10}$ IU/mL above nadir) in HCV RNA at any time-point. Subject will stop all study drugs.
- Confirmed breakthrough or relapse: HCV RNA \geq LLOQ (defined as 2 consecutive HCV RNA measurements \geq LLOQ) at any point after HCV RNA $<$ LLOQ. Subject will stop all study drugs (if applicable).

For the latter 2 criteria, confirmatory testing should be completed as soon as possible. If the investigator feels that a subject who meets one of these criteria should still remain on DAA + pegIFN + RBV or pegIFN + RBV treatment, the subject would only be allowed to remain on DAA + pegIFN + RBV or pegIFN + RBV treatment with approval of the AbbVie Study Designated Physician.

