8.1.5 Resistance Analyses

The genes of interest for population sequencing in this study are those encoding full length NS3/4A and NS5A, while for clonal sequencing they are those encoding NS3 amino acids 1 to 181 and NS5A amino acids 1 to 215. For each DAA target, resistance-associated signature amino acid variants will be identified by AbbVie Clinical Virology. Amino acid positions where resistance-associated variants have been identified in vitro and/or in vivo are: 155, 156, and 168 in NS3 for ABT-450; 28, 30, 31, 58, and

93 in NS5A for ABT-267. This list may be expanded if treatment-emerged resistance-conferring variants are identified at additional amino acid positions in DAA-treated patients. The prototypic reference sequences used for analysis will be H77 for genotype 1a or Con1 for genotype 1b.

Only samples with an HCV RNA level of ≥ 1000 IU/mL will undergo sequence analysis in order to allow accurate assessment of products of amplification. Therefore, if the HCV RNA level at the time of virologic failure is < 1000 IU/mL, the sample closest in time after the failure with an HCV RNA level ≥ 1000 IU/mL will be used. Clonal sequencing of a given target will be performed only if no variants are detected at signature resistance-associated amino acid positions by population sequencing in that sample. In addition, clonal sequencing may be performed if there is a complex mixture of amino acids at one or more signature resistance-associated position that cannot be resolved by population sequencing.

Included time points for analyses on samples from subjects who experience virologic failure (as defined in Section 5.4.1.1) are (1) time of virologic failure or sample closest in time after failure with an HCV RNA level of ≥ 1000 IU/mL, (2) 24 weeks post-DAA treatment, provided that resistance-associated variants were detected by either population or clonal sequencing at the time of failure, and (3) 48 weeks post-DAA treatment, provided that resistance-associated variants were detected by either population or clonal sequencing at post-DAA treatment Week 24.

The following definitions will be used in the resistance analyses:

- Baseline variant: a variant (by population sequencing) in a baseline sample determined by comparison of the amino acid sequence of the baseline sample to the appropriate prototypic reference amino acid sequence for a given DAA target (NS3 or NS5A).

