### **Definitions for Efficacy Endpoints**

Note that a confirmed quantifiable post-treatment value is defined as any two consecutive post-treatment HCV RNA measurements  $\geq$  LLOQ. During treatment, a confirmed quantifiable value is defined as any two consecutive HCV RNA values  $\geq$  LLOQ, either both during treatment or at the final treatment measurement and the next consecutive post-treatment measurement.

**RVR** (Rapid Virologic Response) = HCV RNA < LLOQ at TI Week 4.

**eRVR** (extended rapid virologic response) = HCV RNA < LLOQ at TI Weeks 4 through 12 without a confirmed HCV RNA  $\geq$  LLOQ between TI Weeks 4 and 12.

**Final Treatment Visit Response** = HCV RNA < LLOQ at the end of treatment (i.e., at completion of all study drugs: DAAs, pegIFN, and RBV); this corresponds to the Final Treatment Visit value (see Section 6.0).

**Breakthrough** = confirmed increase from nadir in HCV RNA (two consecutive HCV RNA measurements  $> 1 \log_{10}$  IU/mL above nadir) at any time point during treatment or confirmed HCV RNA  $\geq$  LLOQ after HCV RNA  $<$  LLOQ during treatment. A single breakthrough value ( $\geq$  LLOQ or  $> 1 \log_{10}$  above nadir) followed by lost to follow-up would be considered a breakthrough (i.e., will not require confirmation).

**On-treatment virologic failure = breakthrough** or failure to suppress during treatment (all on-treatment values of HCV RNA  $\geq$  LLOQ ) with at least 6 weeks (defined as active study drug duration  $\geq 36$  days) of treatment.

**SVR24** (referred to as SVR24actual in the protocol) = HCV RNA  $<$  LLOQ in the SVR24 window (24 weeks after the last actual dose of study drug [including DAA, pegIFN, and RBV]) without any confirmed quantifiable ( $\geq$  LLOQ) post-treatment value before or during that SVR window.

**SVR12** (referred to as SVR12actual in the protocol) = HCV RNA  $<$  LLOQ in the SVR12 window (12 weeks after the last actual dose of study drug [including DAA, pegIFN, and RBV]) without any confirmed quantifiable ( $\geq$  LLOQ) post-treatment value before or during that SVR window.

**SVR4** = HCV RNA  $<$  LLOQ in the SVR4 window (4 weeks after the last actual dose of active study drug) without any confirmed quantifiable ( $\geq$  LLOQ) post-treatment value before or during that SVR window.

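### The post-baseline resistance set follows the failure criteria in Protocol 5.4.1.1, which leave out some subjects whom SAP 10.1 counts as virologic failures

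*SAP*

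**What the plan says.** Three definitions of the resistance population or of virologic failure are in force.

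- **All subjects without SVR.** The protocol synopsis and Protocol 5.3.3.3 say: "The following resistance analyses will be performed for subjects who do not achieve SVR".
- **Failure per Protocol 5.4.1.1.** Protocol 8.1.5 says: "Included time points for analyses on samples from subjects who experience virologic failure (as defined in Section 5.4.1.1) are (1) time of virologic failure". SAP 10.6 repeats the restriction: "Included time points for analyses on samples from subjects who experience virologic failure (as defined in Section 5.4.1.1"). Section 5 of the SAP ends at 5.2, so the reference can only mean the protocol section. That section has five criteria. The TI Week 4, TI Week 12 and TI Week 24 criteria rest on one value each. The rise from nadir and the criterion beginning "Confirmed breakthrough or relapse: HCV RNA" each need two consecutive values.
- **Failure per SAP 10.1.** If the last available post-treatment value is at or above LLOQ, "then the subject will be considered a relapse (i.e., will not require confirmation"). A single breakthrough value "followed by lost to follow-up would be considered a breakthrough (i.e., will not require confirmation").

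SAP 10.6 introduces its post-baseline listings with: "The following analyses will be performed on the samples from subjects who experienced virologic failure and have post-baseline resistance data available". Sequencing needs a sample of at least 1000 IU/mL. Baseline variants are listed for every subject whose baseline sample reaches that level, and Protocol 5.3.1.1 has all subjects sequenced at pre-screening. SAP 12.0 updates the signature positions but does not mention the resistance population.

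**The concern.** The efficacy tables and the resistance analysis use different failure sets. The two unconfirmed routes to failure in SAP 10.1 have no counterpart in the two-value criteria of Protocol 5.4.1.1. The subjects who fall between the definitions are not a random subset: they are those who were lost or left before a repeat test.

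Protocol 3.0 says that response on re-exposure to a DAA had not yet been studied. Protocol 3.2 names further resistance as a risk of failing this regimen, and Substudy 3 follows subjects for 48 weeks partly to observe it. Enrolment is up to 35, so failures will probably be few. SAP 10.6 calls a post-baseline variant emerged only if it is seen in two or more subjects of the same subtype. Leaving out one subject can therefore remove a variant from that category, and the linked-variant listing draws on it.

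**Working it through.** The plan states no figure to reproduce. The check applies both definitions to hypothetical HCV RNA histories, with baseline 1,000,000 IU/mL and LLOQ 25 IU/mL.

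**Inputs**
- Protocol 5.4.1.1: TI Week 4 value not below 1,000 IU/mL; less than a 2 log10 fall at TI Week 12; value of 25 IU/mL or more at TI Week 24; two consecutive values more than 1 log10 above nadir; two consecutive values at or above LLOQ after a value below LLOQ.
- SAP 10.1: confirmed breakthrough or relapse; the two unconfirmed routes quoted above; failure to suppress with at least 36 days of treatment.
- SAP 10.6: sequencing only at 1000 IU/mL or more.

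| Case | History | SAP 10.1 | Protocol 5.4.1.1 | Result |
|---|---|---|---|---|
| A | Completer, suppressed; one last post-treatment value of 50,000 | Relapse | No criterion met | Sequenceable, left out |
| B | Completer; two consecutive post-treatment values at or above LLOQ | Relapse | Met | Included |
| C | Suppressed; one on-treatment value of 20,000, then lost | Breakthrough | No criterion met | Sequenceable, left out |
| D | Never below LLOQ; TI Week 4 = 500, TI Week 8 = 400; lost at about day 60 | On-treatment failure (60 is at least 36 days) | No criterion met | Failure sample below 1000, not sequenced under any definition |
| E | TI Week 4 = 1,500; later suppressed, SVR achieved | Not a failure | Met on one value | Included although a responder |

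A and C are counted failures with usable samples that the stated rule leaves out. E shows the opposite mismatch, so the resistance denominator can be smaller or larger than the failure count.

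**Scale.** The documents give no rate for histories like A or C. Let q be the assumed share of such subjects among N = 35. Then P(at least one) = 1 − (1 − q)^35, and the expected number is 35q.

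- q = 0.01: 1 − 0.99^35 = 0.297; 35 × 0.01 = 0.35
- q = 0.02: 1 − 0.98^35 = 0.507; 35 × 0.02 = 0.70
- q = 0.05: 1 − 0.95^35 = 0.834; 35 × 0.05 = 1.75
- q = 0.10: 1 − 0.90^35 = 0.975; 35 × 0.10 = 3.5

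These show only how the result depends on q; they do not estimate it.

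**The case against.** Much can be said for the existing text.

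- **The SAP follows the protocol's statistical section.** A reader might infer that the SAP departed from the protocol. It did not: Protocol 8.1.5 carries the same restriction. The conflict lies inside the protocol, between the synopsis and 5.3.3.3 on one side and 8.1.5 on the other, and the SAP inherits it. The reference to a section absent from the SAP is editorial. This stands, but the conflict still needs resolving.
- **Confirmation is requested.** Protocol 5.4.1.1 says: "For the latter 2 criteria, confirmatory testing should be completed as soon as possible". It applies in follow-up too, so a first positive value at PT Week 48 should prompt a repeat even though no later visit is scheduled. This narrows the gap to subjects who are lost or leave before the repeat.
- **Late relapsers are mostly outside the non-SVR wording.** A completer first positive at PT Week 48 will normally have achieved SVR12 and SVR24. That visit is about 24 + 48 = 72 weeks after the last DAA dose, past the 24- and 48-week post-DAA time points, so at most the failure sample is at stake. This stands. Such a subject is still counted as a relapse in the SAP.
- **Some sequence data remain.** A reader might infer that these subjects are never sequenced. Pre-screening and baseline sequences are kept; only post-baseline analysis is at risk.
- **A milder reading exists.** The sentence introducing the post-baseline listings does not repeat the 5.4.1.1 limit. However, the time-point sentence decides which failure samples are analysed, so the milder reading does not clearly bring these subjects in.
- **The outputs are descriptive.** Resistance is not among the primary or secondary objectives in Protocol 4.1 and 4.2. This stands and limits the weight of the point.

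**Conclusion.** The point holds as a mismatch of definitions. On a literal reading, a failure counted on one unconfirmed value gets no post-baseline resistance analysis even with a sample of at least 1000 IU/mL, while an SVR responder who missed the TI Week 4 threshold can be included. SAP 12.0 gives no sign that either result was intended.

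The number affected cannot be derived from the documents. If 5 to 10 failures are assumed, each omission removes 1/10 to 1/5, or 10–20%, of the failures. A reader might take this as the expected loss, but it is only the weight of one subject under an assumed count and says nothing about how many are omitted. Nor do the documents support saying that 5.4.1.1 requires confirmation throughout: two of its five criteria do, although those two govern relapse and breakthrough.

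The effect is confined to descriptive resistance listings and counts. No primary or secondary estimate or interval changes. The change is still worth making, because the dataset is small, two subjects are enough to define an emerged variant, and the cost is low.

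**What to change.** In SAP 10.6, replace the reference to Section 5.4.1.1 with an explicit population:

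1. all subjects meeting the SAP 10.1/10.5 definitions of breakthrough, on-treatment virologic failure or any relapse, including preterm, late and unconfirmed last-value relapse; and
2. any other subject without SVR who has a post-baseline sample of at least 1000 IU/mL.

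The 1000 IU/mL sequencing threshold stays in force for all of them. Where failure is unconfirmed, use the single available sample as the time-of-failure sample. Flag separately any subject who meets only Protocol 5.4.1.1, so that the resistance denominator can be matched to the failure table. Record in SAP 12.0 how this set reconciles Protocol 5.3.3.3 with Protocol 8.1.5. The criteria in Protocol 5.4.1.1 need no change for this purpose.

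The cost is SAP wording and a few more sequencing assays. Protocol Table 7 already schedules resistance samples at every post-treatment visit, so no new collection is needed.
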